#### Change from baseline

Mean change from baseline in the clinical status on the 9-point ordinal scale to Days 15 and 29 will be analyzed using an analysis of covariance (ANCOVA) model with factors for treatment

group, age, gender, and region, as well as the baseline clinical status as a continuous linear covariate. The estimated treatment differences, p-values, and 95% CIs will be presented.

Missing data at Day 15/29 will not be imputed and thus will be excluded from the analysis.

### **Time to improvement from baseline category**

Time to improvement from baseline category to one less severe category of the ordinal scale will be analyzed using a competing risk analysis framework where death will be treated as a competing risk. Specifically, a proportional hazards model for the subdistribution ([Fine and Gray 1999](#)) of time to improvement will be performed. Same covariates will be used as for the primary analysis. Patients who did not achieve improvement and did not die will be censored at their last clinical status assessment date. The estimated hazard ratios, p-values, and 95% CIs will be presented. The cumulative incidence functions of improvement and death over study days will be plotted by treatment.

In addition, the median time to improvement by treatment as well as the 95% CI will be estimated using the Kaplan-Meier approach, while dead patients will be censored at the maximum follow-up time in the study.

#### **2.7.1.2 Oxygen saturation**

The proportion of patients with no oxygen therapy (defined as having a clinical status score of 0, 1, 2, or 3, or oxygen saturation  $\geq 94\%$  when measured on room air) at Days 15 and 29 will be analyzed using logistic regression models with the same covariates as for the primary analyses, with baseline SpO2/FiO2 added. The estimated odds ratios, p-values, and 95% CIs will be presented.

Missing data at Day 15/29 will not be imputed and thus will be excluded from the analysis.

#### **2.7.1.3 In-hospital outcomes**

Duration of hospitalization (time to hospital discharge) will be analyzed using a competing risk analysis framework (death will be treated as a competing risk). Specifically, a proportional hazards model for the subdistribution ([Fine and Gray 1999](#)) of time to hospital discharge will be performed. Same covariates will be used as for the primary analysis. Patients who were not discharged and did not die will be censored at their last assessment date. The estimated hazard ratios, p-values, and 95% CIs will be presented. The cumulative incidence functions of hospital discharge and death over study days will be plotted by treatment.

In addition, the median time to hospital discharge by treatment as well as the 95% CI will be estimated using the Kaplan-Meier approach, while dead patients will be censored at the maximum follow-up time in the study.

The analyses of mortality rates at Day 15 and at Day 29, and proportion of patients requiring mechanical ventilation by Day 29 are described in [Section 2.5.4](#).

The subgroups of patients with different baseline clinical status will be evaluated for mortality using a similar logistic regression model as described for the primary analysis, replacing the baseline clinical status ( $\leq 3, \geq 4$ ) by baseline clinical status as a categorical variable, and adding

the interaction term of baseline clinical status and treatment. The point estimate and 95% CI for odds ratio for each subgroup will be summarized.

#### **2.7.1.4 National Early Warning Score (NEWS2)**

Time to discharge or to a National Early Warning Score (NEWS2) of  $\leq 2$  and maintained for 24 hours (whichever comes first; maintained for 24 hours is defined as score being  $\leq 2$  for two days in a row as the score is collected once per day) will be analyzed using a competing risk analysis framework (death will be a competing risk). A proportional hazards model for the subdistribution will be performed. Patients who did not achieve discharge, nor had a NEWS2 of  $\leq 2$  maintained for 24 hours, nor died will be censored at their last assessment date. The estimated hazard ratios, p-values, and 95% CIs will be presented. The cumulative incidence functions will be plotted by treatment by competing risks. The model will include the same covariates as in the primary analysis, with baseline NEWS2 score added.

In addition, the median time to hospital discharge or to a NEWS2 of  $\leq 2$  and maintained for 24 hours by treatment as well as the 95% CI will be estimated using the Kaplan-Meier approach, while dead patients will be censored at the maximum follow-up time in the study.

Summary statistics of change from baseline to Days 3, 5, 8, 11, 15, and 29 in the NEWS2 will be provided by treatment. No missing data will be imputed.

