Study design	This is a randomized, double-blind, placebo-controlled, 29-day, multi-center study to assess the efficacy and safety of ruxolitinib + SoC therapy, compared with placebo + SoC therapy, in patients aged ≥12 years with COVID-19 pneumonia.
Study population	Approximately 402 males and females ages 12 and older with COVID-19 pneumonia.

Key Inclusion criteria
	
 • Patient or guardian/health proxy must provide informed consent (and assent if applicable) before any study assessment is performed. • Male and female patients aged ≥ 12 years (or \geq the lower age limit allowed by Health Authority and/or Ethics Committee/Institutional Review Board approvals). • Patients with coronavirus (SARS-CoV-2) infection confirmed by polymerase chain reaction (PCR) test or another rapid test from the respiratory tract prior to randomization. • Patients currently hospitalized or will be hospitalized prior to randomization. • Patients, who meet at least one of the below criteria: 
 • Pulmonary infiltrates (chest X ray or chest CT scan); • Respiratory frequency ≥ 30/min; • Requiring supplemental oxygen; • Oxygen saturation $\leq 94\%$ on room air; • Arterial oxygen partial pressure (PaO₂)/ fraction of inspired oxygen (FiO₂) < 300mmHg (1mmHg=0.133kPa) (corrective formulation should be used for higher altitude regions (over 1000m)).

Key Exclusion criteria
	
 • History of hypersensitivity to any drugs or metabolites of similar chemical classes as ruxolitinib. • Presence of severely impaired renal function defined by serum creatinine > 2 mg/dL (>176.8 μmol/L), or have estimated creatinine clearance < 30 ml/min measured or calculated by Cockcroft Gault equation or calculated by the updated bedside Schwartz equation. • Suspected uncontrolled bacterial, fungal, viral, or other infection (besides COVID-19). • Currently intubated or intubated between screening and randomization. • In intensive care unit (ICU) at time of randomization. • Intubated or in ICU for COVID-19 disease prior to screening. • Patients who are on anti-rejection, immunosuppressant or immunomodulatory drugs (i.e. tocilizumab, ruxolitinib, canakinumab, sarilumab, anakinra). • Unable to ingest tablets at randomization. • Pregnant or nursing (lactating) women.

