5.1 Inclusion criteria

Participants eligible for inclusion in this study must meet **all** of the following criteria:

1. Patient or guardian/health proxy must provide informed consent (and assent if applicable) before any study assessment is performed.
2. Male and female patients aged ≥ 12 years (or \geq the lower age limit allowed by Health Authority and/or Ethics Committee/Institutional Review Board approvals).
3. Patients with coronavirus (SARS-CoV-2) infection confirmed by polymerase chain reaction (PCR) test or another rapid test from the respiratory tract prior to randomization.
4. Patient is currently hospitalized or will be hospitalized prior to randomization.
5. Patients, who meet **at least one** of the below criteria:
 - Pulmonary infiltrates (chest X ray or chest CT scan);
 - Respiratory frequency ≥ 30 /min;
 - Requiring supplemental oxygen;
 - Oxygen saturation $\leq 94\%$ on room air;
 - Arterial oxygen partial pressure (PaO₂)/ fraction of inspired oxygen (FiO₂) < 300 mmHg (1mmHg=0.133kPa) (corrective formulation should be used for higher altitude regions (over 1000m)).

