16.3 Appendix 3: National Early Warning Score 2 (NEWS2)

Physiological parameter	Score						
	3	2	1	0	1	2	3
Respiration rate (per minute)	≤8		9–11	12–20		21–24	≥25
SpO ₂ Scale 1 (%)	≤91	92–93	94–95	≥96			
SpO ₂ Scale 2 (%)	≤83	84–85	86–87	88–92 ≥93 on air	93–94 on oxygen	95–96 on oxygen	≥97 on oxygen
Air or oxygen?		Oxygen		Air			
Systolic blood pressure (mmHg)	≤90	91–100	101–110	111–219			≥220
Pulse (per minute)	≤40		41–50	51–90	91–110	111–130	≥131
Consciousness				Alert			CVPU
Temperature (°C)	≤35.0		35.1–36.0	36.1–38.0	38.1–39.0	≥39.1	

SpO₂ = oxygen saturation.

The oxygen saturation should be scored according to either the SpO₂ Scale 1 or 2 presented in the table above. The SpO₂ Scale 2 is for patients with a target oxygen saturation requirement of 88%-92% (e.g., in patients with hypercapnic respiratory failure related to advanced lung diseases, such as chronic obstructive pulmonary disease [COPD]). This should only be used in patients confirmed to have hypercapnic respiratory failure by blood gas analysis on either a prior or their current hospital admission.

The decision to use the SpO₂ Scale 2 should be made by the treating physician and should be recorded in the eCRF. In all other circumstances, the SpO₂ Scale 1 should be used.

For physiological parameter “Air or Oxygen?”: Any patients requiring the use of oxygen or other forms of ventilation to maintain oxygen saturations and support respiration should be assigned a score of 2.

The consciousness level should be recorded according to the best clinical condition of the patient during the assessment. Patients who are assessed as “Alert” (A) should be assigned a score of 0. Patients assessed as “New Confusion” (C), “Responsive to Voice” (V), “Responsive to Pain” (P), or “Unconscious” should be assigned a score of 3.

Scores should be assigned for respiratory rate, systolic blood pressure, pulse, and temperature according to the table above.

NEWS2 values will be calculated electronically throughout the study by the Sponsor based upon entry of vital sign parameters by the investigator in the appropriate eCRF.

Example Case Calculation:

An 82-year-old lady was admitted, tested positive to COVID-19 and admitted to high dependency unit for non-invasive ventilation. Her taken observations and corresponding NEWS2 score are as follows:

Physiological Parameter	Observation	Component Score
Respiratory rate (per min)	26	3
Oxygen saturation (SpO ₂ %)	95%	1
Supplemental Oxygen	Yes	2

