### 2.2.1 Subgroup of interest

Subgroup analyses are conducted to assess consistency of the treatment effect among the subgroups, without multiplicity adjustments. The following subgroups will be evaluated for the primary endpoint, i.e., defined as the proportion of patients who die, develop respiratory failure (require mechanical ventilation), or require ICU care by Day 29:

- Age category (< 18, 18 - < 65, ≥ 65 years)
- Gender (male, female)
- Race (White, Asian, Black, other)
- Ethnicity (Hispanic, non-Hispanic)
- Region (North America, East Europe, West Europe, and Latin America)
- Body mass index (BMI) ( $\leq 30.0 \text{ kg/m}^2$ ,  $> 30.0 \text{ kg/m}^2$ )
- Baseline steroid use (Yes, No)

- Baseline clinical status based on 9-point scale (3, 4, 5)
- Baseline hypertension (Yes, No)
- Baseline diabetes (Yes, No)
- [REDACTED]
- Time between onset of COVID-19 symptoms and randomization ( $\leq 10$ ,  $> 10$  days)

Baseline steroid use is defined as usage between onset of symptoms and randomization (inclusive). Baseline hypertension/diabetes is defined as “Yes” if patients have the comorbidity ongoing at randomization.

In addition to the primary endpoint, subgroups of patients with different baseline clinical status based on 9-point scale (3, 4, 5) will be evaluated for the following endpoints:

- Mortality by Day 29

• [REDACTED]

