## 2.7 Analysis of secondary efficacy objectives

### 2.7.1 Secondary endpoints

No multiplicity adjustment will be carried out for secondary analyses described below.

All analysis of secondary endpoints will be performed on the RAS.

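### Patients who enter with NEWS2 already at 2 or less can meet the time-to-NEWS2 event within about Days 1 to 3, mostly without improving, which dilutes any true effect in the single hazard ratio.

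*SAP*

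**What the plan says.** SAP 2.7.1.4 analyses time to discharge or to a sustained NEWS2 of 2 or less, whichever is first, with death as a competing risk. The 24-hour requirement becomes a score of 2 or less "for two days in a row as the score is collected once per day". The same event definition, without the two-day operational rule, is in Protocol Table 2-1 and Protocol 12.5.1.4.

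- **Population.** SAP 2.7.1: "All analysis of secondary endpoints will be performed on the RAS". No baseline NEWS2 threshold is set, and no fall from baseline is required.
- **Model.** A subdistribution hazards model: "The model will include the same covariates as in the primary analysis, with baseline NEWS2 score added". Kaplan-Meier medians by arm are also planned.
- **Entry.** The Protocol summary and Protocol 5.1 admit "Patients, who meet at least one of the below criteria". There are five criteria, and lung infiltrates on imaging are one of them.
- **Scoring.** Under Protocol Appendix 3, patients who need oxygen or ventilation to keep up saturation and "support respiration should be assigned a score of 2". Imaging is not scored.
- **Baseline severity.** SAP 2.2.1 plans subgroups at clinical status 3 (in hospital, no oxygen), 4 and 5. SAP Section 4 reports that very few patients were recruited at status 5.

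**The concern.** The related objective is efficacy in terms of change in NEWS2, and the endpoint will be read as time to recovery. A patient who starts at 2 or less and stays there meets it with no change at all. The neighbouring ordinal-scale endpoint (SAP 2.7.1.1) avoids this by requiring improvement from the baseline category.

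Such patients have their events at about the same time in both arms, before a drug effect could show, and these events feed the one treatment hazard ratio. A real benefit in patients with room to improve would then be understated. If half or more of an arm started at 2 or less, that arm's Kaplan-Meier median would also sit near Day 2 and say little about recovery.

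**Working it through.** **1. The plan's own figures.** The documents give no effect size or power for this endpoint. Their only power statement is for the primary endpoint (SAP Section 3), and it reproduces with an unpooled two-proportion Z-test on 134 and 268 patients. For 50% against 35%: SE = √(0.50×0.50/134 + 0.35×0.65/268) = 0.0521, and power = Φ(0.15/0.0521 − 1.96) = 82%, as stated. The other rows also match. From this I take only N = 402, 2:1 allocation and two-sided 5%.

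**2. Can patients enter at 2 or less?** Scores from Protocol Appendix 3, SpO2 Scale 1, with all items not mentioned at 0:

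| Patient | NEWS2 |
|---|---|
| Infiltrates, room air, SpO2 96% or more | 0 |
| Infiltrates, room air, SpO2 94–95% (1), pulse 91–110 (1) | 2 |
| Room air, SpO2 92–93% | 2 |
| On oxygen (2), SpO2 96% or more | 2 |
| Respiratory rate 30 or more | at least 3 |

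Only the respiratory-rate criterion rules out a score of 2 or less while it is met.

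**3. When would they have the event?** The Day 1 assessments are made before the first dose (Protocol Section 8), and scores are daily. If the Day 1 score may be the first of the pair, the pair is Days 1–2. If only post-baseline scores count (SAP 2.1.1.3, after first dose), it is Days 2–3. The SAP does not say which applies, nor which day of the pair is the event date. The event therefore falls on Day 1, 2 or 3.

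**4. Why the covariate does not help.** The model is h(t) = h₀(t)·exp(β·treatment + γ·baseline NEWS2 + …). The term γ lets low-score patients have a higher hazard in both arms. It leaves one β for everyone, so patients whose event time does not depend on treatment pull β towards 0.

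**5. Size, assumed hazard ratio 1.4 in the other patients.** Assumptions: 90% of low-score patients have the event on Day 2, placebo median about 9 days, no deaths, proportional hazards model on treatment and baseline NEWS2 with Efron ties, 400 trials per setting.

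| Share at 2 or less | Estimated HR | Power |
|---|---|---|
| 10% | 1.39 | 80% |
| 20% | 1.36 | 74% |
| 30% | 1.31 | 67% |
| 40% | 1.27 | 53% |

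Further runs at a 30% share and the same hazard ratio gave 1.28–1.29 (58–61%) and 1.27 (57%). The range across runs is about 1.38–1.39 at 10% and 1.27–1.31 at 30%. On the log scale the loss is 1 − ln(1.39)/ln(1.4) = 2% to 1 − ln(1.38)/ln(1.4) = 4% at a 10% share. At 30% it is 1 − ln(1.31)/ln(1.4) = 20% to 1 − ln(1.27)/ln(1.4) = 29%.

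**6. A second set of assumptions.** Daily hazard ratio 1.5, 8% deaths among patients above 2 (kept in the risk set to Day 29), all low-score patients with the event on Day 2, 200 trials per setting (error about 3 points on power):

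| Share at 2 or less | All randomised: HR, power | Baseline above 2 only: HR, power |
|---|---|---|
| 0% | 1.34, 73% | 1.34, 73% |
| 10% | 1.30, 63% | 1.33, 65% |
| 30% | 1.23, 45% | 1.34, 58% |
| 50% | 1.18, 29% | 1.36, 48% |

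The comparator here is 1.34, not 1.5, because daily rounding and deaths already lower the estimate. If only 80% of low-score patients have the event on Day 2 and the rest respond to treatment, the full-set estimate is 1.27 at 30% and 1.25 at 50%.

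**7. No true effect.** The mean estimate was 1.00 at a 0% share and 0.99 at 30%, so the estimate is not biased. The null runs were too few (200 each), and used a variance the SAP does not name, to say anything about false-positive rates.

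**8. Comparing remedies at a 30% share, hazard ratio 1.4 above 2.** Counting only discharge for low-score patients depends on what treatment does to their discharge:

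| Analysis | HR | Power |
|---|---|---|
| Discharge-only, discharge HR 1.4 | 1.41 | 87% |
| Discharge-only, discharge HR 1.2 | 1.34 | 77% |
| Discharge-only, discharge HR 1.0 | 1.26 | 52% |
| Baseline above 2 only | 1.41 | 70% |

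A separate run gave 1.26 and 57% for discharge-only with no discharge effect, and 1.39 and 66% for the restriction.

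**The case against.** The strongest reply is that the effect may be negligible. The share is unknown, and at 10% the loss is about 0.01 to 0.02 on the hazard ratio. The dilution is towards no effect, the endpoint is one of many secondary endpoints without multiplicity control, and no power is claimed for it. Recovery relative to baseline is also measured by time to a one-category improvement, the responder analyses and NEWS2 change from baseline. All of this stands, and it keeps the point small.

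A reader might infer that every low-score patient has the event at once whatever the treatment. The documents do not support that: some will worsen on Day 2 or 3, and the 80% to 100% immediate-event rates above are simulation inputs. A reader might also infer from the planned status 3 subgroup, or from the few patients at status 5, that the share is large. Those facts make low scores plausible but give no number, since respiratory rate, pulse, temperature, blood pressure and SpO2 also score.

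Finally, one might want to redefine the event as discharge only for low-score patients. That puts two different events into one hazard ratio, departs from the protocol's endpoint and helps only if treatment also speeds their discharge. Discharge already has its own analysis in SAP 2.7.1.3.

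**Conclusion.** The point holds in a limited form. As written, the rule can count baseline status as recovery. If treatment works in patients above 2, the common hazard ratio is diluted, and the baseline covariate does not remove this. With an assumed hazard ratio of 1.4 the loss is small at a 10% share and material at 30% (about 1.27–1.31, power about 57–67%). These sizes rest on the assumed share, event rates and immediate-event proportion, and on models that left out age, gender, region and baseline clinical status.

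A reader might take this as a threat to the trial's conclusion or as a source of a spurious benefit. Neither follows: the primary analysis does not use this endpoint, and with no true effect the estimate stays near 1. It is a cheap improvement.

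**What to change.** Before unblinding, in SAP 2.7.1.4:

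1. Keep the protocol-defined analysis in all randomised patients.
2. Add a pre-specified analysis of the same endpoint in patients with baseline NEWS2 above 2, using the same model and Kaplan-Meier medians, and state that the endpoint is interpreted as recovery from that analysis.
3. Report the number and percentage with baseline NEWS2 of 2 or less by arm.
4. State whether the pre-dose Day 1 score can be the first of the two days, and which day is the event date.
5. Do not adopt a discharge-only rule for low-score patients.

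The cost is a few sentences, one baseline flag, one repeat of existing output and a note in SAP Section 4. The added analysis has fewer patients (at a 30% share, about 0.7 × 402 = 281). In the simulations at a 30% share its power was nonetheless no lower than that of the full set, but the main gain is an estimate that does not depend on the share.

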#### **2.7.1.5 SpO2/FiO2 ratio**

Summary statistics of change from baseline to Days 15 and 29 in SpO2/FiO2 ratio will be provided by treatment. In addition, the following categorization will be done:

- Severity of acute respiratory distress syndrome (ARDS): normal:  $> 314$ ; mild (235 - 314); moderate: 150 - 234; severe:  $< 150$

## **2.8 Safety analyses**

Safety summaries include only data from the treatment-emergent period with the exception of baseline data which will also be summarized where appropriate (e.g. change from baseline summaries).

All safety analysis will be performed on the Safety Set.

### **2.8.1 Adverse events (AEs)**

Adverse events will be summarized by treatment group.

The number (and percentage) of subjects with treatment-emergent adverse events, defined as events start after the first dose of double-blind medications or events present prior to start of double-blind treatment but increase in severity based on preferred term and up to last study visit, will be summarized in the following ways:

- by treatment and preferred term (PT).
- by treatment, SOC and PT.

- by treatment, SOC, PT and maximum severity (based on CTCAE grades, categorized as Grades 3-4, Grade 5, and All grades). For this summary an AE with missing CTCAE grade will be included in the 'All grades' column of the summary tables.

Separate summaries by SOC and PT will be provided for:

- AEs suspected to be study medication related
- deaths
- serious adverse events (SAEs)
- AEs leading to treatment discontinuation
- AEs leading to dose interruptions and/or adjustments

Further SAEs will be summarized by PT.

Unless otherwise specified, SOCs will be sorted alphabetically and, within each SOC, the PTs will be sorted in descending order of frequency in the ruxolitinib + SoC arm. A subject with multiple adverse events within a SOC or PT is only counted once towards the total of the SOC or PT.

Listings will be provided for all AEs, SAEs, AEs leading to treatment discontinuation, and deaths.

### **2.8.1.1 AE reporting for CT.gov and EudraCT**

For the legal requirements of clinicaltrials.gov and EudraCT, two required tables on treatment emergent adverse events which are not serious adverse events with an incidence greater than 2% and on treatment emergent serious adverse events and SAE suspected to be related to study treatment will be provided by system organ class and preferred term on the safety set population.

If for a same patient, several consecutive AEs (irrespective of study treatment causality, seriousness and severity) occurred with the same SOC and PT:

- a single occurrence will be counted if there is  $\leq 1$  day gap between the end date of the preceding AE and the start date of the consecutive AE
- more than one occurrence will be counted if there is  $> 1$  day gap between the end date of the preceding AE and the start date of the consecutive AE

For occurrence, the presence of at least one SAE / SAE suspected to be related to study treatment / non SAE has to be checked in a block e.g., among AE's in a  $\leq 1$  day gap block, if at least one SAE is occurring, then one occurrence is calculated for that SAE.

The number of deaths resulting from SAEs suspected to be related to study treatment and SAEs irrespective of study treatment relationship will be provided by SOC and PT.

